**a. Age (minors, elderly):**

We will not be recruiting minor participants for this pilot study. At present, the mRSF is not regularly provided to children, so we will not be recruiting participants under the age of 18 for this study.

**b. Gender:**

We will not exclude participation based on gender. Both males and females are welcome to participate in this study.

**c. Ethnic and racial minority populations:**

We will not exclude participation based on ethnicity or race.

**3. What characteristics (inclusion criteria) must subjects have to be in this study? (Answer for each subject group, if different.)**

Inclusion criteria include: 18 or more years of age, non-dysvascular unilateral transtibial amputation, prosthetic user for >1 year, are scheduled to receive a prosthesis with a mRSF, able to walk continuously for at least 6 minutes with or without an assistive device, able to read and write English.

**4. What characteristics (exclusion criteria) would exclude subjects who are otherwise eligible from this study? (Answer for each subject group, if different.)**

Exclusion criteria include any health condition that would limit use of a prosthesis (e.g., skin breakdown), ability to safely walk for at least 6 minutes (e.g., heart disease), or participation (current or planned over the study period) in another research study that may affect the fit or function of his/her prosthesis.

**5. Describe the subject recruitment strategies you will use for each group of subjects. (You should obtain letters of cooperation from agencies, institutions, or others involved in subject recruitment for your research records. Do not send these to HSD or the IRB.)**

Study participants will be exclusively recruited from Davidson Prosthetics, the only local prosthetics facility that routinely provides prostheses with ESF and mRSF to people with LLA. Informed consent will be obtained from all participants.

**6. Explain who will approach subjects to take part in the study and how this will be done to protect subjects' privacy. (Attach letters of cooperation from agencies, institutions or others involved in subject recruitment.)**

Flyers will be posted at Davidson Prosthetics with study information and the phone number of the study coordinator (**Appendix 4**). In addition, [name] will let potential participants know about the study and provide the phone number of our study coordinator. Potential participants can call our study coordinator to get more information about the study, decide if they are interested in participating, and schedule their first study session (**Appendix 5**).

**7. Explain what steps you will take during the recruitment process to minimize potential coercion or the appearance of coercion.**

Their prosthetic care provider ([name]) will only inform potential participants about the study. All recruitment and enrollment procedures will be conducted by study investigators/coordinators. All interested participants will be informed that participation (or not) is completely voluntary and will in no way affect the clinical care they receive. No members of our study team are or will be involved in the clinical care of potential participants or participants.

8. Will you give subjects gifts, payments, services without charge, or extra course credit?  No  Yes If yes, explain:

Subjects will receive \$30 for every hour of participation in the screening session (Session 1). Participants will receive \$50 for every hour of participant in data collection sessions (Sessions 2 & 3). Participants will be paid after each session.

9. Will any of the subjects or their third-party payers be charged for any study procedures?  No  Yes If yes, explain:

N/A

10. **UW Locations and research sites.** Provide the following information in list or table format for all UW locations at which any research procedures will occur. Be sure to consider: screening, recruiting, consenting, observation, intervention, data collection, data analysis, specimen analysis, and location of any consultants and collaborators.

- Geographical location and/or address
- Name of organization, agency, group, site, institution
- What procedures will occur at each location (how the location is involved in the research)
- Whether subject contact or interaction will occur at each site
- Whether consenting of subjects will occur at each site
- Whether each site, or individuals at the site, will obtain, use, or have access to coded or individually identifiable private information about subjects for research purposes

	Site 1:	Site 2:
	University of Washington Department of Rehabilitation Medicine Health Sciences Building, BB tower, 8 th floor	Davidson Prosthetics, LLC [name]
Screening	X (Screening will be done by study investigators/staff over telephone)	
Recruiting	X (The study will be described to potential participants by study investigators/staff. Potential participants will have the opportunity to ask questions and decide if they would like to schedule a data collection session at this time)	X ([name] will post flyers and let potential participants know about the study)
Consenting	X (Study investigators, [name] and [name], will obtain informed consent at the data collection appointment, prior to data collection activities)	N/A
Observation	N/A	N/A
Intervention	N/A	N/A
Data Collection	X (Study investigators, [name] and [name], will perform all data collection activities)	N/A
Data Analysis	X (Study investigators, [name] and [name], will	N/A

	perform all data analysis activities)	
--	---------------------------------------	--

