Commercially-available running-specific feet (RSF) like the Össur Cheetah (Össur, Reykjavik, Iceland) allow people with LLA to participate in athletic activities and sporting events. RSF provide significantly enhanced performance, compared to traditional ESF, by extending the length and increasing the stiffness of the prosthetic keel (forefoot). RSF also do not include a heel, as they are used only for running activities. Although transtibial runners with RSF exhibit endurance levels similar to non-amputees, the RSF design does not allow the biomechanical movements or provide the stability needed to use the foot for walking (over level or uneven terrain).

A Seattle-area prosthetist, [name], currently provides many of his active LLA patients with a modified running-specific foot (mRSF). The mRSF combines the running keel (forefoot) of a RSF with the walking heel of a ESF. The mRSF can then be used for walking, running, and other routine daily activities. [name] has fit and provided this prosthetic foot on over 100 of his patients. Preliminary feedback suggests that users experience improved overall function and high satisfaction with the device. However, empirical evidence is needed to support prescription of this prosthetic foot at other clinical facilities. The goal of this study is therefore to evaluate endurance, walking performance, mobility, and perceived exertion of transtibial prosthesis users (i.e., study participants) walking with a conventional ESF and the mRSF. Results will be compared to determine if the mRSF provides superior performance to the ESF, which is commonly prescribed to most active individuals with LLA.

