**B. RESEARCH PROCEDURES INVOLVED.**

1. Provide a complete description of: a. the study design, and b. sequence and timing of all study procedures that will be performed, e.g., volume of blood, size of biopsy, drug administration, questionnaire, name of psychological test. Provide this information for each phase of the study (pilot, screening, intervention and follow-up). **Use lay language.** Attach study flow sheet, if available.

We will conduct a study to compare endurance, walking performance, mobility, and perceived exertion of participants with transtibial amputation wearing two different prostheses: (1) a prosthesis with a modified Running Specific Foot (mRSF), and (2) a prosthesis with a Energy Storing Foot (ESF). To maximize study resources, we will recruit participants who will be receiving from their prosthetist the mRSF prosthesis as part of their normal clinical care. We will fabricate a duplicate prosthesis with the ESF as part of this study to be used as a comparison.

*Note: Both the mRSF and ESF included in this study are devices that people with LLA use daily in their normal lives outside of this study. These feet (and other components included in the prostheses created for this study) are class I devices and exempt from U.S. Food and Drug Administration premarket notification procedures.*

We will conduct a randomized crossover study to compare endurance, energy expenditure, and reported health of participants with transtibial amputation wearing prostheses with the mRSF and ESF described above. Study participants will be randomly assigned to the first foot condition (i.e. ESF or mRSF). To standardize test conditions, the participant's prosthetist ([name]) will fabricate two comparable prostheses with identical (i.e. duplicated) prosthetic sockets, interfaces, and suspension mechanisms. The same socket cannot be used for both prostheses because of the unique, direct-lamination attachment of the mRSF to the socket. The duplicate socket will be fitted with common ESF, the Ossur Vari-flex foot. We have obtained written commitments from Ossur to donate prosthetic components and from Davidson Prosthetics to donate time and materials needed to fabricate the duplicate sockets and test prostheses. Participants will be asked to wear the same athletic shoes for all sessions in order to standardized footwear between tests.

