Participants will be recruited from their local prosthetist's office (Davidson Prosthetics, Federal Way, WA). Davidson Prosthetics is the sole location for recruitment as this is the only provider of the mRSF in the Northwestern United States.

Participants will be asked to come to the University of Washington Assessment and Training Laboratory (ATL) for three test sessions. Participation in the study will require participants attend three visits over the course of about three months, totaling approximately 7.5 hours.

Session 1: At the first session, we will screen participants, explain the study to them, and obtain informed consent (**Appendix 1**). Participants who agree will then be administered a baseline survey and perform initial speed testing. The baseline survey will include non-identifiable, medical, and demographic questions we will use to characterize the study sample (**Appendix 2**). Participants will then be asked to walk on a treadmill for 6 minutes to determine their comfortable walking speed. The treadmill is equipped with full-length handrails that allow the participant to steady him/herself as needed. A researcher will be next to the subject at all times to assist the subject if he or she were to become distressed.

Participants will be given blinded control of the treadmill speed for the first 30 seconds of testing in order to select their preferred speed. Each participant's comfortable speed will be noted and used as a reference for the metabolic testing (see Session 2 and 3, described below). Slow and fast speeds will be self-selected using an identical method (blinded control of the treadmill adjustment). Participants will be asked to perform a 6 minute practice trial at their self-selected fast speed to ensure the participant is capable of sustaining the speed without undo stress. If a participant is unable to sustain the set speed for the entire 6 minutes, he/she may reduce speed as desired, and a weighted average of the start and end fast speeds will be used for treadmill testing in Sessions 2 and 3. We will also give participants a step activity monitor to wear on their prosthesis. The activity monitor is a small, unobtrusive sensor about the size of a pager that is worn on the prosthesis and measures steps taken by the participant while they are away from the lab. Participants will be shown how to attach the activity monitor to their prosthesis by study investigators. Session 1 is expected to take about 1.5 hours.

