Session 2: The second session will be performed after participants use the randomly-assigned ESF or mRSF prosthesis for a period of 1 month. Upon arrival at the lab, study

staff will remove the activity monitor and ask the participant to complete a self-report survey (**Appendix 2**) to evaluate their perceived performance, health, and satisfaction with their prosthesis. The survey will be administered on a tablet computer (iPad) and includes the following standardized instruments selected to measure participants' mobility, fatigue, balance confidence, activity restrictions, and satisfaction:

- Prosthetic Limb Users Survey of Mobility - PLUS-M measures respondents' self-reported mobility with a prosthesis. The PLUS-M was developed by the investigators in a prior study to address methodological limitations present in existing mobility measures. We will administer the PLUS-M computer adaptive test (CAT) to achieve the greatest precision of measurement and ease respondents' burden (i.e., CAT requires participants answer fewer questions than would taking the entire survey).
- PROMIS - Fatigue - PROMIS-F measures symptoms and effects of fatigue on respondents' ability to execute daily activities over a 1-week recall period. We will also administer PROMIS-F by CAT.
- Activities Specific Balance Confidence Scale - ABC measures respondents' confidence in performing basic ambulatory activities. We will administer a version of the ABC recommended to ease administration and improve scoring. All 16 questions of the ABC will be administered (CAT not available).
- Trinity Amputation and Prosthesis Experience Scales - Revised - TAPES-R is a multidimensional health instrument that measures activity restrictions and satisfaction with a prosthesis. We will administer 19 TAPES-R questions (CAT not available).

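### Does admitting both established mRSF users and patients new to the foot spoil the crossover comparison?

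*Protocol*

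**What the plan says.** Section VIII.D, item 3 of the Protocol requires a "prosthetic user for >1 year, are scheduled to receive a prosthesis with a mRSF", alongside age, amputation type, walking ability and English. The exclusions in item 4 concern health conditions and participation in other studies. Neither item mentions the habitual foot or earlier use of an mRSF.

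Section VIII.B.1 describes the source of participants: "we will recruit participants who will be receiving from their prosthetist the mRSF prosthesis as part of their normal clinical care". It does not say whether this is a first mRSF or a replacement. Recruitment is from a single clinic, described in section VIII.D, item 5 as "the only local prosthetics facility that routinely provides prostheses with ESF and mRSF to people with LLA". According to section VIII.A its prosthetist "has fit and provided this prosthetic foot on over 100 of his patients".

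The design is a two-period crossover: "Study participants will be randomly assigned to the first foot condition (i.e. ESF or mRSF"). The comparator is one fixed model: "The duplicate socket will be fitted with common ESF, the Ossur Vari-flex foot". Each foot is worn before it is tested: "The second session will be performed after participants use the randomly-assigned ESF or mRSF prosthesis for a period of 1 month", and the second foot is likewise worn for a month before Session 3. At Session 1, "The baseline survey will include non-identifiable, medical, and demographic questions we will use to characterize the study sample". That survey is Appendix 2, which is not among the pages at hand.

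**The concern.** A crossover removes stable differences between participants, and randomising the order balances period effects. Familiarity with the habitual foot is neither of these. A long-standing mRSF user may still do better on the mRSF after a month on each foot. A patient coming from an ESF may still do better on the ESF. In both sequences that advantage stays attached to the foot, so it goes straight into the mRSF minus ESF contrast.

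Because both kinds of patient are eligible and no mix is given, the sign of the term cannot be known in advance. The stated purpose (sections VIII.A and VIII.E.5) is evidence for offering the mRSF elsewhere, and many patients elsewhere would be new to it. A favourable result obtained mainly in established users might not carry over to them. Residual ESF familiarity in a sample of new users might hide a benefit.

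**Working it through.** **Inputs.** From the Protocol: at most 24 completers (section VIII.D.1), two periods, and about one month on each foot before testing (section VIII.B.1). The document gives no SD, target effect, alpha, power, patient mix or familiarity effect, so the 24 cannot be re-derived; the point does not depend on it. Assumed for illustration: no true foot effect on 6-minute walk distance, SD of the paired difference 30 m within each group, two-sided 5% t test.

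**The term.** Let p be the share of prior mRSF users, f their remaining mRSF advantage and g the remaining ESF advantage of patients new to the mRSF. Averaging the two sequence means removes the period effect and leaves

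expected estimate = true effect + p·f − (1 − p)·g.

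With f = g the added term is f(2p − 1). At 5 m and 0, 6, 12, 18 or 24 prior users it is −5, −2.5, 0, +2.5 and +5 m.

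**Size.** Rejection rate in either direction when there is no true effect, by number of prior mRSF users among 24:

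| Remaining advantage | 0 | 6 | 12 | 18 | 24 |
|---|---|---|---|---|---|
| f = g = 0 | 5% | 5% | 5% | 5% | 5% |
| f = g = 2 m | 6% | 5% | 5% | 5% | 6% |
| f = g = 5 m | 12% | 6% | 5% | 6% | 12% |
| f = g = 10 m | 35% | 11% | 4% | 11% | 35% |
| f = g = 20 m | 88% | 24% | 2% | 24% | 88% |
| f = 5 m, g = 0 | 5% | 5% | 7% | 9% | 12% |
| f = 10 m, g = 0 | 5% | 6% | 12% | 21% | 35% |

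A separate simulation in SD units, with 12 participants per sequence and a period effect of 0.5 SD, agrees. With f = g = 0.3 SD (0.3 × 30 = 9 m) the mean estimates were −0.29, −0.15, 0.00, +0.15 and +0.30 SD, with rejection in 29%, 10%, 4%, 10% and 29%. The period effect cancelled; the familiarity term did not.

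**What the table shows.** The term always lies between −g and +f, so a mixed sample can never be further off than the worse of the two unmixed ones. With f = g, mixing shrinks it. Large distortion needs 10 m or more to survive a month of wear and a lopsided mix.

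**Would the possible changes help?**

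- *Stratifying the sequence by prior foot.* The sequence does not appear in p·f − (1 − p)·g, so the pooled term is unchanged.
- *Excluding prior users.* This sets p = 0 and leaves −g in full. It helps if g is near zero (last two rows: 5% at p = 0) and hurts if f and g are alike (at 10 m, 35% with none against 11% with 6). It also narrows recruitment at the only clinic.
- *Estimating by group.* SE = 30/√m is 12.2 m for m = 6, 8.7 m for m = 12 and 7.1 m for m = 18. The t-based 95% half-widths are 31.5, 19.1 and 14.9 m, all wider than the 5 to 10 m in question. For the difference between groups, which estimates f + g, SE = 30·√(1/6 + 1/18) = 14.1 m for a 6/18 split and 30·√(1/12 + 1/12) = 12.2 m for 12/12. Power is then 10% to 12% for 10 m and 27% to 35% for 20 m.

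**The case for a change.** The best case for acting is that eligibility belongs in the protocol, so an unseen analysis plan does not answer the gap. A clinic with more than 100 mRSF fittings may well send replacement patients. One sentence on eligibility and one baseline item would cost almost nothing. The investigators also intend to combine these data with later studies (section VIII.G.2), so an unrecorded habitual foot would carry forward.

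Part of this stands. The text does leave prior mRSF users eligible without saying so, and the algebra is right. The rest is weaker:

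- The patients already fitted are active prosthesis users in general. The protocol does not show how many meet the criteria or are due for a new limb, so entry of established users is permitted but not demonstrated.
- It is not shown that the habitual foot goes unrecorded. The baseline survey exists to characterise the sample and its content is not visible. The component information to be obtained from the prosthetist (section VIII.H.3.a) may or may not reach back to the earlier limb, because the words limiting it to the study period can be read as applying only to the problems experienced.
- The ESF side of the term may be small, since the study ESF is a single model that need not be what new users wore before.

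**Conclusion.** No change follows. The observation is accurate, but it does not identify a wrong result. The pooled contrast is a valid answer for patients scheduled to receive an mRSF at this clinic, which is the population the protocol defines. Broad eligibility is a fair choice for a single-clinic pilot of at most 24 completers, and a month on each foot is a reasonable guard against familiarity.

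Under the assumed 30 m SD the effect is negligible at about 2 m of remaining advantage and modest at 5 m. It becomes large only at 10 m or more with an unbalanced mix. The documents support none of these values over the others, and zero is possible. No available change removes the term whatever f and g are, and a split by prior foot would be too imprecise to confirm or dismiss it. What remains is descriptive detail: prior foot belongs with the sample characteristics and in the discussion of how far the result reaches new users, where analysts would sensibly put it if the baseline survey captures it.

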## E. RISKS AND BENEFITS

In order to approve the research the IRB must find that risks are reasonable in relation to anticipated benefits, if any, to subjects, and the importance of the knowledge that may reasonably be expected to result.

1. Describe nature and degree of risk of possible injury, stress, discomfort, invasion of privacy, and other side effects from all study procedures, drugs and devices (standard and experimental), interviews and questionnaires. Include psycho-social risks as well as physiological risks. Include risks of withholding standard care or procedures if this is the case. Do not reference the consent form.

Participants will be asked to walk for about 70 minutes total for this study (a maximum of 6 minutes at a time, and 30 minutes maximum per session). Because they are being asked to walk, there is the risk that they could become fatigued during the study procedures. In addition, there is a risk of falling. However, these risks are no larger than the risks that study participants generally undertake when walking outside of this study.

2. Explain what steps you will take to minimize risks of harm and to protect subjects' rights and welfare. (If you will include protected groups of subjects (minors; fetuses in utero; prisoners; pregnant women; unviable neonates; neonates of uncertain viability; decisionally impaired or economically or educationally disadvantaged subjects) please identify the group(s) and answer this question for each group. Please also complete the SUPPLEMENT: Protected and/or Vulnerable Populations.)

This study will not require participants to perform activities at a level of endurance that they would not typically do outside of the study session. To minimize risks of fatigue and falling during the study session, the participants will be asked to take breaks after each walking measure is collected. The maximum time that each participant will be asked to walk continuously is 6 minutes. They are also instructed to take a break, including a sitting break, at any time during the data collection session, including in the middle of walking measures. If at any time it appears that the participant is at risk of falling or other harm, the data collection session will be stopped.

3. Is it possible that you will discover a subject's previously unknown condition (disease, suicidal intentions, genetic predisposition, etc.) as a result of study procedures?  No  Yes If yes, explain how you will handle this situation.
4. Describe the anticipated benefits of this research for individual subjects in each subject group. If none, state "None."

None

5. Describe the anticipated benefits of this research for society.

The mRSF is a promising advancement in prosthetic technology. However, currently, [name] is one of few prosthetists in the United States that is providing this foot. Empirical evidence that supports its provision for people with LLA will help the mRSF become available to others who may benefit from its use.

